3.2.2. Measures of Patient Well-Being

3.2.2.1. Overall Survival

While OS provides an ultimate measure of patient well-being, it has not routinely been used as the primary endpoint in CLL clinical trials. Unlike PFS, it does not specifically measure drug-mediated tumor control, and thus provides only an indirect assessment of treatment effect. Depending upon the treatment setting, long OS times in patients with CLL can preclude use of this endpoint as an efficient method for understanding drug benefits. In both the front-line and recurrent disease settings, post-study treatments can influence OS in unpredictable ways, potentially confounding differences between treatment groups.

However, given the life-threatening nature of systemic malignancy, documentation of OS is customary in oncology therapeutic clinical trials, including those evaluating subjects with recurrent CLL {Keating 2002a, Wierda 2010}. Evaluation of OS in this study continues the survival assessment from the primary study (Study GS-US-312-0116). The study program as a whole (considering both the primary randomized trial and secondary extension study) offers the potential to better understand OS and causes of death in a frail population of patients with both CLL, considering the consequences of the disease and comorbidities.

3.2.2.2. Health-Related Quality of Life

Direct patient reporting of outcomes using standardized methods has become an increasingly important component of therapeutic assessment. Evaluation of patient-reported outcomes (PROs) is particularly relevant in patients who cannot be cured of disease {Reeve 2007}. PRO questionnaires have been previously used in CLL to understand how patients differ from the general population in terms of health concerns {Eichhorst 2007, Else 2008, Holzner 2004, Shanafelt 2007}, to understand differences in perceptions of well-being in younger vs older patients {Else 2008, Levin 2007}, to determine how treatment affects HRQL {Catovsky 2007, Efficace 2008, Eichhorst 2007}, and to assess the pharmacoeconomic cost of improvements in HRQL {Stephens 2005}.

Patients with CLL have overtly impaired well-being relative to comparable controls {Eichhorst 2007, Else 2008, Holzner 2004, Shanafelt 2007}. Fatigue is cited as a common complaint, being present in the substantial majority of patients. Impairment of HRQL prior to any treatment is apparent in those with B symptoms or in patients with anemia, supporting the concept of initiating treatment when patients experience symptomatic disease. Factors associated with lower overall HRQL have included older age, greater fatigue, severity of co-morbid health conditions, advanced stage, and ongoing treatment for CLL {Shanafelt 2007}. Younger patients appear to

have worse emotional and social well-being but older patients experience worse physical HRQL {Levin 2007}. In comparative evaluation of chemotherapy-containing regimens, differences in HRQL between therapies (eg, fludarabine vs fludarabine-cyclophosphamide vs chlorambucil) reflected differences in toxicity while improved HRQL was associated with greater efficacy {Catovsky 2007, Eichhorst 2007}.

In this study, it is postulated that idelalisib-mediated tumor control will be correlated with greater positive changes in HRQL and that assessments of the drug's safety profile will be supported by HRQL evaluations. The FACT-Leu (Appendix 2) has been selected to evaluate such outcomes for the study. The FACT-Leu comprises a general HRQL measure for patients receiving cancer treatment that yields a total score and subscales for physical, functional, social/family and emotional well-being {Cella 1993} and a diagnosis-specific measure for patients with leukemia {Webster 2002}. The FACT-Leu was developed to assess symptoms (eg, fevers, chills, night sweats, nodal swelling, fatigue) specifically relevant to patients with leukemia. FACT instruments have documented psychometric properties {Brucker 2005, Cella 2005, Cella 1993, Victorson 2008, Webster 2002}.

The FACT-Leu instrument is available in appropriate languages for this study. FACT-Leu data will be obtained at baseline and during each investigational clinic visit during treatment. Having FACT-Leu data concurrent with tumor response information will allow an evaluation of the potential relationship between tumor response and symptomatic changes as reported by patients. To avoid biasing HRQL results, the FACT-Leu will be administered at each visit before other procedures are performed and before any study information is conveyed to the subject.

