3.1.2. Patient Well-Being

- Overall survival (OS) defined as the interval from start of study therapy to death from any cause
- Change from baseline in HRQL domain and symptom scores based on the Functional Assessment of Cancer Therapy: Leukemia (FACT-Leu) (see Appendix 2)
- Changes from baseline in Karnofsky performance status defined as the change from baseline in the performance status (see Appendix 3)

CONFIDENTIAL Page 38 21 September 2017

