As a baseline, the last value obtained prior to the baseline reference date for efficacy endpoints, as defined in Section 3.5.1, will be used. The mean and change from baseline in mean scores to each subsequent assessment will be summarized for the subscale and composite scores. The best change from baseline during the study, defined as the highest positive value among all post-baseline visits minus the baseline value, will also be summarized.

Each subject's FACT-Leu subscales (ie, PWB, EWB, SWB, and FWB) scores at each assessment will be compared to their baseline scores. The minimally important difference (MID) for these subscales is 3 points {26297}. An increase of at least 3 points will be required as a definition of symptom improvement. The cumulative distribution function (CDF) of best change from baseline will be provided. For the MID improvement comparison, subjects with baseline score > 55 will be excluded (ie, subjects with no room for improvement). Time to symptom response will be assessed by defining the first occurrence of symptom improvement as an event. Subjects who do not experience a symptom improvement compared to baseline will be censored at their last available FACT-Leu assessment time.

A data listing for each individual item, the subscale scores, and the composite scores will be presented for each subject at each time point.

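### The SAP's symptom-improvement rule omits the leukemia-specific FACT-Leu subscale, so four of the five symptoms the protocol names have no item in it, and its ceiling exclusion can never apply

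*Protocol*

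**What the plan says.** Protocol 3.2.2.2 describes FACT-Leu as a general cancer quality-of-life measure with four well-being subscales plus a leukemia-specific part. Of the instrument's purpose it says "The FACT-Leu was developed to assess symptoms (eg, fevers, chills, night sweats, nodal swelling, fatigue) specifically relevant to patients with leukemia". Having these data alongside tumor response, it adds, "will allow an evaluation of the potential relationship between tumor response and symptomatic changes as reported by patients". The endpoint in Protocol 3.1.2 is "Change from baseline in HRQL domain and symptom scores".

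SAP 6.1.2.9 scores five subscales, the fifth being the 17-item LeuS (headed Additional Concerns in Protocol Appendix 2). The responder paragraph then narrows: "FACT-Leu subscales (ie, PWB, EWB, SWB, and FWB) scores at each assessment will be compared to their baseline scores". It continues "The minimally important difference (MID) for these subscales is 3 points", and "An increase of at least 3 points will be required as a definition of symptom improvement". From this it builds a time-to-event analysis: "Time to symptom response will be assessed by defining the first occurrence of symptom improvement as an event". For the same comparison it drops subjects with a baseline above 55, on the ground that they cannot improve further.

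Outside this paragraph LeuS is kept. It enters the Trial Outcome Index and the FACT-Leu total, and the planned summaries of mean, change and best change cover the subscales generally. SAP Appendix 1 lists a cumulative distribution of best change (Figure 2.1.5) and a change-from-baseline plot (Figure 2.2.5) for Additional Concerns.

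**The concern.** The responder rule carries the word symptom, yet its list of subscales is closed (ie, not eg) and omits the one written for leukemia symptoms. A colleague shown a symptom-response rate or a time to symptom response in a CLL trial will read it as relief of B symptoms and nodal swelling. The rule has no item for either. It does take in subscales about social support, mood and daily function.

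The ceiling exclusion raises a second doubt. A cut at 55 does not fit any of the four listed subscales, so the paragraph is unclear about which scores it was written for.

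At stake is what the responder output can be said to show, and whether it can serve the protocol's aim of relating tumor response to symptomatic change.

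**Working it through.** **Inputs.** Item counts (PWB 7, SWB 7, EWB 6, FWB 7, LeuS 17), the 3-point threshold and the cut at 55 come from SAP 6.1.2.9. The 0 to 4 item scoring and item content come from Protocol Appendix 2.

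**Reproducing the SAP's ranges.** Maximum = 4 × items. Trial Outcome Index = 28 + 28 + 68 = 124. FACT-G = 28 + 28 + 24 + 28 = 108. Total = 108 + 68 = 176. All three match the SAP.

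| Scale | Items | Maximum | 3 points as share of range | Highest baseline that can gain 3 | Can exceed 55? |
|---|---|---|---|---|---|
| PWB | 7 | 28 | 10.7% | 25 | no |
| SWB | 7 | 28 | 10.7% | 25 | no |
| EWB | 6 | 24 | 12.5% | 21 | no |
| FWB | 7 | 28 | 10.7% | 25 | no |
| LeuS | 17 | 68 | 4.4% | 65 | yes |

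**What the rule covers.** It uses 7 + 7 + 6 + 7 = 27 of 44 items. The omitted part is 17/44 = 38.6% of items and 68/176 = 38.6% of points.

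**Where the five named symptoms are asked.** Fevers (BRM3), chills (BRM2), night sweats (ES3) and lumps or swelling (LEU1) are in Additional Concerns only. Fatigue has a counterpart in PWB (GP1, energy) as well as LeuS items. Some FWB item wording is illegible in the text available, but the SAP reverses no FWB item, so none is a negatively worded complaint. Four of five therefore have no item in the rule.

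**Two illustrations.**
- Fevers, chills, night sweats and swelling each fall from 3 to 0, and nothing else changes. After reversal each item gains 3. LeuS rises 4 × 3 = 12 and the four listed subscales rise 0, so there is no symptom improvement.
- Three SWB items each rise one step. SWB rises 3, which meets the definition.

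**The ceiling exclusion.** The listed maxima are 28, 24, 28 and 28, so no subject can exceed 55 on them. Subjects at 26 to 28 on PWB, SWB or FWB, or 22 to 24 on EWB, cannot gain 3 points, yet they remain as certain non-responders. Only LeuS or a composite can exceed 55.

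**A LeuS threshold.** The documents give none. As an assumption, keep the same share of range: 3/28 × 68 = 7.3, or 3/24 × 68 = 8.5, so about 7 to 9 points. The cut at 55 should not move to LeuS unchanged: with a 7-point threshold, baselines of 56 to 61 can still respond (68 − 7 = 61); with 9 points, 56 to 59 can.

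**The case against.** The strongest reply is that little depends on this paragraph. Neither Protocol 3.1.2 nor SAP 6.1.1 lists time to symptom response as an endpoint. SAP Appendix 1 has no table or figure titled for it, and SAP 3.5.2 makes the analyses descriptive with no formal comparison between groups. LeuS is already summarised, and the proportion ever improving by any chosen number of points can be read from Figure 2.1.5. All of that stands and limits the consequence. It does not repair the definition: the analysis text still promises a symptom response and a time to it, and a distribution of best change gives no time to first improvement.

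A reader might infer that the endpoint measures no CLL symptoms. The documents do not support that. PWB asks about energy, pain, nausea and feeling ill, and Protocol 3.2.2.2 names fatigue as a common CLL complaint. Relief of fevers or sweats might also show indirectly through feeling ill.

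A reader might also infer that a gain on any one of the four subscales makes a subject a responder. The SAP states no such pooled rule, and its planned distributions are one per subscale. On the separate reading, a social gain would be reported as a social-subscale result. It would still sit under the symptom-improvement label.

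Finally, LeuS is not a pure symptom scale. Five of its 17 items, worth 20 of 68 points, concern worry, uncertainty, emotional ups and downs, and isolation. A 7-point gain is possible without symptom change. This argues for care in labelling LeuS, not for leaving it out.

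**Conclusion.** The point holds as a defect of definition and labelling in one SAP paragraph. As written, the symptom-improvement and time-to-symptom-response analyses have no item for four of the five symptoms the protocol names, and they attach the symptom label to social, emotional and functional gains. Separately, the exclusion at 55 has no effect on any listed subscale and leaves certain non-responders in the comparison. How many subjects that involves cannot be known from the documents.

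The omission does not extend to the other FACT-Leu analyses, and it affects no formal comparison. Nor do the documents show a deliberate decision to exclude LeuS: a cut that only LeuS or a composite can reach leaves the intended scope unclear. The item and range arithmetic rests on the documents alone. The 7 to 9 point LeuS threshold rests on proportional scaling, which is an assumption.

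**What to change.** In SAP 6.1.2.9:

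1. Report gains of at least 3 points separately for each of the four general subscales. Call EWB, SWB and FWB gains well-being improvement, and keep PWB as a symptom-related scale.
2. Add LeuS to the symptom-improvement and time-to-symptom-response analyses with its own threshold, justified by the sponsor. Until then, show results over a range such as 5 to 9 points, which spans the scaled values of 7.3 and 8.5 and includes lower cuts. Note that LeuS also contains worry and emotional items.
3. Replace the cut at 55 with a scale-specific ceiling: exclude a baseline above the scale maximum minus the threshold. That is above 25 for PWB, SWB and FWB, above 21 for EWB, and above 61 or 59 for LeuS at 7 or 9 points.

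The cost is revised wording, one added responder and Kaplan-Meier output listed in SAP Appendix 1, and the work of justifying a LeuS threshold. No new data are needed, since LeuS is already collected and scored.

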3.2.2.3. Changes in Performance Status

Performance status evaluation provides an integrated assessment of patient well-being before, during, and after treatment and, ideally, may indicate how drug efficacy and toxicity affect patient functioning. In patients with CLL performance status can be predictive of PFS or OS {Hallek 1996, Sorensen 1997, Youngson 1995}.

In this study, it is hypothesized that idelalisib-mediated tumor control will be correlated with changes in performance status and that assessments of the drug's safety profile might be supported by performance status evaluations. The well-established, reliable, and validated Karnofsky performance score {Karnofsky 1949, Schag 1984, Yates 1980} (see Appendix 3) will be employed in the trial for characterization of the subject population and repeated assessment of performance status.

3.2.3. Pharmacodynamic Markers of Drug Activity and Resistance

In CLL, disease-related perturbations in inflammatory status can be clinically overt; patients often develop bothersome B symptoms (fevers, night sweats, and weight loss) that are characteristic of excessive systemic inflammation {Redaelli 2004}. Consistent with such disease manifestations, the PI3K δ /AKT/mTOR pathway is constitutively overactive in circulating CLL cells {Coutre 2011}. In addition, chemokines and cytokines that are markers of aberrant B-cell trafficking or perturbations in inflammation are overexpressed by CLL tissues or by stromal cells

and circulate in plasma {Burger 2010, Coutre 2011}. In Phase 1 studies of idelalisib it has been confirmed that idelalisib largely normalizes AKT phosphorylation and induces dose-dependent reductions in plasma concentrations of circulating chemokines and cytokines in patients with CLL {Coutre 2011}.

In this study, it is hypothesized that incremental changes in these biomarkers provide direct evidence of mechanism-specific idelalisib effects on PI3K δ activity or indirectly document drug effects on overall tumor cell volume. In either case, improvements in these pharmacodynamic measures provide corroborative evidence in support of idelalisib pharmacological activity; conversely, worsening of these biomarkers may indicate acquisition of resistance to idelalisib. In addition, it is possible that disease-or inflammation-related biomarkers may provide corollary information relating to the adverse effects of idelalisib on the liver; such data might allow better prediction of which subjects might be most susceptible to ALT/AST elevations during idelalisib treatment. Finally, it can also be postulated that genetic, protein, or metabolic changes in CLL cells could provide signatures that would correlate with drug sensitivity and resistance.

Based on these considerations, this study will evaluate PI3K/AKT/mTOR pathway activation status in CLL cells. For this purpose, blood will be evaluated by flow cytometry using a clinically validated assay {Hoellenriegel 2011}. CLL cells will be identified using anti-CD5 and anti-CD19 antibodies. AKT activation will be determined by quantifying phosphorylation at the Ser473 and Thr308 AKT sites using specific anti-pAKT Thr308 and anti-pAKT Ser473 antibodies. Additional assessments of PI3K/AKT/mTOR pathway signaling (eg, evaluating phosphorylation state for other downstream enzymes) may also be explored.

Plasma will be collected for assessment of circulating concentrations of relevant chemokines and cytokines with a particular focus on CCL2, CCL3, CCL4, CXCL12, CXCL13, CCL17, CCL19, CCL21, CCL22, sCD40 ligand, tumor necrosis factor-α, and C-reactive protein. In addition serum markers of iron metabolism (eg, hepcidin, iron, ferritin, transferrin) that might provide markers linking disease-related inflammation with perturbations of liver iron and sensitivity to liver injury will be evaluated {Ferrucci 2010, Nemeth 2003}. Clinically validated assays (eg, enzyme-linked immunosorbent assays [ELISAs]) will be used to measure circulating concentrations of chemokines and cytokines at baseline and during the course of idelalisib therapy.

CLL cell deoxyribonucleic acid (DNA), ribonucleic acid (RNA), and protein will be collected at baseline and at the conclusion of a subject's treatment on study. DNA and RNA samples will be analyzed using gene array technologies to evaluate for changes in DNA mutations or in RNA expression patterns that might be associated with intrinsic or acquired resistance to study treatments. Similarly, protein will be evaluated for state-specific changes in protein phosphorylation to evaluate for differences in pathway activation at baseline or during therapy that might be associated with differences in response or in acquisition of resistance to therapy.

3.2.4. Assessments of Exposure

3.2.4.1. Study Drug Administration and Compliance

Evaluation of study drug administration and compliance provides context for assessments of safety, pharmacokinetics, and pharmacological activity. Evaluations of treatment administration and modifications from planned therapy document the influence of treatment-emergent adverse events on prescribing practice. Compliance assessment offers a general indication of patients' acceptance of therapy, integrating factors of tolerability, palatability, and convenience.

In this study, information regarding planned treatment and modification from planned treatment (eg, dose reductions and interruptions) will be kept. The compliance of the subject will be verified by accounting for used and unused drug.

3.2.4.2. Pharmacokinetics

Given the intent of this protocol to assess longer-term dosing, collection of plasma for idelalisib concentrations is important for evaluating exposure over time. These data may allow correlations of exposure with measures of efficacy, toxicity, and resistance. Because the idelalisib pharmacokinetic profile has been well characterized in Phase 1 studies, limited plasma sampling will be performed in this study. Samples will be collected pre-dose and 1.5 hours post-dose relative to the morning administration of idelalisib. Based on discussions with investigators, collecting more than 2 samples in the morning is not considered reasonable given the need to minimize time requirements for study participants and to avoid substantial inconvenience for clinic staff.

Evaluation of idelalisib plasma concentrations will be performed using liquid chromatography with tandem mass spectrometry. The method has been fully validated in the context of prior Phase 1 studies. Plasma samples will be retained for potential later analyses of idelalisib metabolites.

3.2.5. Evaluations of Safety

In defining the therapeutic relevance of a drug in a particular clinical setting, it is imperative that its safety profile be fully characterized. As is conventional in all clinical studies, proper description of each adverse event or laboratory abnormality requires an understanding of the type, incidence, timing, severity, and relatedness to study drug. While information on all reported adverse events will be collected, listed, and summarized, particular focus will be placed on monitoring and reporting adverse events and laboratory abnormalities that were encountered in the prior toxicology studies and clinical experience with idelalisib. Safety parameters of specific interest in reporting study results will include those relating to bone marrow function, dermatological events, gastrointestinal inflammation, infection, pulmonary events (eg, pneumonia/pneumonitis), and liver injury. Additional scrutiny will be applied to Grade 3-4 adverse events, to adverse events causing interruption or discontinuation of idelalisib, and to serious adverse events.

In addition, the protocol will evaluate for potential adverse idelalisib effects on laboratory parameters of immune function; the absolute number of CD4+, CD5+,CD8+, CD16/CD56+, CD19+, and CD20+ cells will be assessed by flow cytometry. Serum concentrations of IgA, IgE, IgG, and IgM will be obtained.

For consistency of interpretation, adverse events will be coded using the standard Medical Dictionary for Regulatory Activities (MedDRA) [http://www.meddramsso.com]), and the severity adverse events and laboratory abnormalities will be graded using the well-defined Common Terminology Criteria for Adverse Events (CTCAE), Version 4.03 (http://evs.nci.nih.gov/ftp1/CTCAE/CTCAE_4.03_2010-06-14_QuickReference_8.5x11.pdf). Standard definitions for seriousness will be applied (see Section 8.1.2).

3.2.6. Pharmacoeconomic Measures

It is increasingly important to understand the potential cost implications of introducing a new medication into patient care for CLL {Hornberger 2012, Main 2010}. In order to analyze the pharmacoeconomic consequences of idelalisib administration, data will be collected regarding the health status of subjects and regarding health care resource utilization.

Heath status information will be obtained with the EQ-5D, which is a self-administered, generic, indirect utility measure {The EuroQol Group 1990} (Appendix 4). The EQ-5D consists of a visual analogue scale on which subjects are asked to rate their current overall health status and 5 single-item dimensions which ask subjects to rate their health in terms of mobility, self-care, usual activities, pain/discomfort and anxiety/depression. For each of the 5 items, patients must choose between 3 levels of difficulty in accomplishing tasks in that dimension. The visual analog scale is then used in combination with the dimension scores to generate a health utility score that can be incorporated into analyses of cost effectiveness. The EQ-5D has been successfully used in the evaluation of patients with B-cell and other cancers {Doorduijn 2005, Witzens-Harig 2009, Yang 2010}.

The EQ-5D instrument is available in appropriate languages for this study. EQ-5D data will be obtained at baseline and during each investigational clinic visit during treatment. The EQ-5D will be administered immediately after administration of the FACT-Leu instrument, before other procedures are performed and before any study information is conveyed to the subject. The EQ-5D instrument takes only 5 minutes to complete.

Health care resource utilization data collection will be based on information provided in the eCRFs and will be focused on the most relevant direct medical resource utilization such as physician visits, laboratory tests, medications (including dose and route), medical procedures, interventions (eg, transfusions), and hospitalizations.

The basic approach will be to combine the resource utilization data from the trial with data on unit prices (collected separately) to estimate total costs. The costs will be described relative to the health care findings as measured by duration of tumor control, the symptom-free survival period, and/or utility outcomes or some other appropriate measure of clinical benefits.

